4 OBJECTIVES AND ENDPOINTS

Table 4-1: Objectives and Endpoints

Objectives	Endpoints
Primary 
To assess the safety and tolerability of cabiralizumab as monotherapy in subjects with advanced solid tumors.	
Incidence of AEs, SAEs, AEs meeting protocol-defined DLT criteria, AEs leading to discontinuation, death and laboratory abnormalities in monotherapy cohorts
Secondary 
To assess the safety of cabiralizumab in combination with nivolumab in subjects with advanced solid tumors and hematologic malignancies.To characterize the PK profile of cabiralizumab administered alone and in combination with nivolumab.To characterize the immunogenicity of cabiralizumab and nivolumabTo assess the preliminary anti-tumor activity of cabiralizumab administered alone and in combination with nivolumab in subjects with advanced solid tumors.To assess the preliminary anti-tumor activity of cabiralizumab administered in combination with nivolumab in subjects with hematologic malignancies.	
Incidence of AEs, SAEs, AEs leading to discontinuation, death and laboratory abnormalitiesSummary measures of PK parameters (Section 9.5) of cabiralizumabIncidence of ADA to cabiralizumab and nivolumabBOR, DOR assessed per RECIST 1.1 by investigatorBOR, DOR assessed by IMWG Response criteria by investigator
	

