The Follow-Up Phase begins when the decision to discontinue a subject from all treatment is made. Subjects will be followed for drug-related toxicities until these toxicities resolve, return to baseline, or are deemed irreversible. All adverse events will be documented for a minimum of 100 days after the last dose of study medication. The study design schematic is presented in Figure 5.1-1 and Figure 5.1-2.

Figure 5.1-1: Dose Escalation Schematic

[figure not shown]
[figure not shown]

Figure 5.1-2: Study Design Schematic

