9.2 Adverse Events

The definitions of an AE or serious adverse event (SAE) can be found in [Appendix 3](#).

AEs will be reported by the participant (or, when appropriate, by a caregiver, surrogate, or the participant's legally authorized representative).

The investigator and any designees are responsible for detecting, documenting, and reporting events that meet the definition of an AE or SAE and remain responsible for following up AEs that are serious, considered related to the study treatment or the study, or that caused the participant to discontinue before completing the study.

Contacts for SAE reporting specified in [Appendix 3](#)

9.2.1 *Time Period and Frequency for Collecting AE and SAE Information*

The collection of nonserious AE information should begin at initiation of study treatment until within 100 days of discontinuation of dosing, at the timepoints specified in the Schedule of Activities ([Section 2](#)). Nonserious AE information should also be collected from the start of a placebo lead-in period or other observational period intended to establish a baseline status for the participants.

Investigator Brochure (IB) represent the Reference Safety Information to determine expectedness of serious adverse events for expedited reporting. Following the participant's written consent to participate in the study, all SAEs, whether related or not related to study drug, must be collected, including those thought to be associated with protocol-specified procedures.

All SAEs must be collected that occur during the screening period and within 100 days of discontinuation of dosing. If applicable, SAEs must be collected that relate to any later protocol-specified procedure (e.g., a follow-up skin biopsy).

The investigator must report any SAE that occurs after these time periods and that is believed to be related to study drug or protocol-specified procedure.

- Medical occurrences that begin before the start of study treatment but after obtaining informed consent will be recorded on the appropriate section of the eCRF section.
- All SAEs will be recorded and reported to Sponsor or designee within 24 hours, as indicated in [Appendix 3](#).
- The investigator will submit any updated SAE data to the sponsor within 24 hours of this being available.

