 - On-treatment AEs will be defined as AEs with an onset date and time on or after the date and time of the first dose of study treatment (or with an onset date on or after the day of first dose of study treatment if time is not collected or is missing). For subjects who are off study treatment, AEs will be included if event occurred within a safety window of 30 days (or 100 days depending on the analysis) after the last dose of study treatment. No “subtracting rule” will be applied when an AE occurs both pre-treatment and post-treatment with the same preferred term and grade.
 - On-treatment evaluations (laboratory tests, pulse oximetry and vital signs) will be defined as evaluations taken after the day (and time, if collected and not missing) of first dose of study treatment. For subjects who are off study treatment, evaluations should be within a safety window of 30 days (or 100 days depending on the analysis) after the last dose of study treatment.

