7.6.1 Deaths

Deaths will be summarized by cohort:

- All deaths, reasons for death.
- Deaths within 30 days of last dose received, reasons for death.

A by-subject listing of deaths will be provided for the all enrolled subjects population.

7.6.2 *Serious Adverse Events*

Serious adverse events will be summarized by cohort:

- Overall summary of SAEs by worst CTC grade (any grade, grade 3-4, grade 5) presented by SOC/PT.
- Overall summary of drug-related SAEs by worst CTC grade (any grade, grade 3-4, grade 5) presented by SOC/PT.

All analyses will be conducted using the 30-day safety window.

A by-subject SAE listing will be provided for the “enrolled subjects” population.

7.6.3 *Adverse Events Leading to Discontinuation of Study Therapy*

AEs leading to discontinuation will be summarized by cohort:

- Overall summary of AEs leading to discontinuation by worst CTC grade (any grade, grade 3-4, grade 5) presented by SOC/PT.
- Overall summary of drug-related AEs leading to discontinuation by worst CTC grade (any grade, grade 3-4, grade 5) presented by SOC/PT.

The analyses will be conducted using the 30-day safety window.

A by-subject AEs leading to discontinuation listing will be provided.

7.6.4 *Adverse Events*

Adverse events will be summarized by cohort.

The following analyses will be conducted using the 30 days safety window only:

- Overall summary of any AEs by worst CTC grade (1, 2, 3, 4, 5, not reported, total) presented by SOC/PT.
- Overall summary of any non-serious AEs presented by SOC/PT.
- Overall summary of drug-related AEs by worst CTC grade (1, 2, 3, 4, 5, not reported, total) presented by SOC/PT.

The following analyses will be conducted using the 30 days safety window and repeated using the 100 days safety window:

- Overall summary of drug-related AEs by worst CTC grade (any grade, grade 3-4, grade 5) presented by SOC/PT.

A by-subject AE Listing will be provided.

7.6.5 *Other Events of Interest*

OEOI will be summarized by cohort for each category.

The following analyses will be conducted using the 100-day safety window:

- Overall summary of OEOI by worst CTC grade (any grade, grade 3-4, grade 5) presented by Category / PT
- Overall summary of drug-related OEOI by worst CTC grade (any grade, grade 3-4, grade 5) presented by Category / PT

A by-subject listing of OEOI will be provided.

7.6.6 *Laboratory Parameters*

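### No SAE table and no overall all-cause AE table uses the 100-day window, although the protocol collects these events for 100 days after the last dose

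*SAP*

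**What the plan says.** **Endpoint.** Protocol Section 4 gives the primary endpoint as "Incidence of AEs, SAEs, AEs meeting protocol-defined DLT criteria, AEs leading to discontinuation, death and laboratory abnormalities in monotherapy cohorts". It attaches no time window. The combination cohorts have a similar secondary endpoint, without the DLT component.

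**Collection.** Protocol 9.2.1 states "All SAEs must be collected that occur during the screening period and within 100 days of discontinuation of dosing", and for non-serious events "The collection of nonserious AE information should begin at initiation of study treatment until within 100 days of discontinuation of dosing". Protocol 5.1 adds "All adverse events will be documented for a minimum of 100 days after the last dose of study medication". Table 2-2 schedules follow-up visits at 28 and 100 days after the last dose.

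**Tabulation.** SAP 6.1 allows either 30 or 100 days after the last dose, depending on the analysis. The choice is then made table by table:

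- SAP 7.6.2, for both SAE summaries: "All analyses will be conducted using the 30-day safety window".
- SAP 7.6.4, for the all-cause AE summary by worst grade, the non-serious AE summary and the drug-related AE summary by individual grade: "The following analyses will be conducted using the 30 days safety window only".
- SAP 7.6.4, for one further table, drug-related AEs by grouped grade: "The following analyses will be conducted using the 30 days safety window and repeated using the 100 days safety window".
- SAP 7.6.5 uses 100 days for the all-cause and drug-related OEOI summaries.
- SAP 7.6.1 tabulates all deaths without a window, and separately those within 30 days.

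By-subject SAE and AE listings are also planned, with no 30-day limit stated for them.

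**The concern.** Safety is the primary objective, and the protocol follows every subject to day 100 to observe it. The SAP treats the later period as informative for drug-related AEs and for OEOI but not for SAEs, and gives no reason for the difference.

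Two things are at stake. First, the reported SAE incidence can be lower than the incidence the trial actually observed. Second, the tables do not line up. A drug-related serious event on day 45 after the last dose counts as a drug-related AE in the 100-day table but not as a drug-related SAE anywhere, and no 100-day table separates serious from non-serious events.

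The all-cause tables matter here because the trial is open-label and has no control group. They are the summaries that do not depend on the investigator's judgement of causality, and they are the ones held to 30 days.

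**Working it through.** The plan states no figure to reproduce, so the check compares windows and then sizes the gap.

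**Step 1. Windows side by side**

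| Summary | SAP section | Window after last dose |
|---|---|---|
| SAEs, all-cause | 7.6.2 | 30 days |
| SAEs, drug-related | 7.6.2 | 30 days |
| AEs, all-cause, by worst grade | 7.6.4 | 30 days |
| AEs, drug-related, by individual grade | 7.6.4 | 30 days |
| AEs, drug-related, by grouped grade | 7.6.4 | 30 and 100 days |
| OEOI, all-cause and drug-related | 7.6.5 | 100 days |
| Deaths | 7.6.1 | No window, plus 30 days |
| Collection of SAEs and non-serious AEs | Protocol 9.2.1 | 100 days |

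**Step 2. Where an SAE with onset on days 31-100 ends up**

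SAP 7.1.1 treats an SAE as an AE that the investigator flagged serious, and counts an AE with missing causality as drug-related. It follows that:

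- *Drug-related, or causality missing:* absent from both SAE tables. It is counted in the 100-day drug-related AE table without a seriousness label, and in the OEOI tables if its term is on that list.
- *Unrelated, OEOI term:* absent from the SAE table and the all-cause AE table. It is counted in the 100-day all-cause OEOI table, again without a seriousness label.
- *Unrelated, not an OEOI term, non-fatal:* in no incidence table. It appears in the listings only.
- *Fatal:* the death is counted in the table of all deaths, although the event is still absent from the SAE tables.

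**Step 3. Size of the gap**

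Post-dose collection days outside the SAE tables: 100 - 30 = 70, and 70/100 = 70%. This share concerns the post-dose period only. The treatment period is fully covered.

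Subjects are counted once (SAP 7.1.1), so a late SAE changes incidence only if that subject had no SAE inside the 30-day window. For one such subject the shift is 1/n:

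- n = 3 (smallest monotherapy cohort): 1/3 = 33.3 points
- n = 6 (full monotherapy cohort, or initial combination cohort): 1/6 = 16.7 points
- n = 12 (expanded combination cohort, or both monotherapy cohorts at six): 1/12 = 8.3 points

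**Step 4. How likely at least one such subject is**

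The documents give no rate, so the per-subject probability p of such a late SAE is assumed. The chance of at least one is 1 - (1 - p)^n:

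| Assumed p | n = 6 | n = 12 |
|---|---|---|
| 5% | 1 - 0.95^6 = 26.5% | 1 - 0.95^12 = 46.0% |
| 10% | 1 - 0.90^6 = 46.9% | 1 - 0.90^12 = 71.8% |
| 20% | 1 - 0.80^6 = 73.8% | 1 - 0.80^12 = 93.1% |

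**Step 5. After the change**

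The repeated tables would cover all 100 post-dose collection days instead of 30.

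**The case against.** The case for leaving the SAP alone has real substance.

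- *The window is pre-specified and breaks no protocol rule.* The 100-day rule governs collection. Neither the endpoint table nor protocol 10.3.2 sets a tabulation window. This stands: a reader might infer that the SAP contradicts the protocol, and it does not.
- *Late drug-related events are tabulated.* A reader might infer that late drug-related SAEs reach no incidence table. They do, through the 100-day drug-related AE table and, where the term applies, the OEOI tables, which SAP 4.1 names among its primary endpoints. What they lose is their identification as serious.
- *The choice can be defended.* These subjects have advanced, refractory or relapsed cancer, and events after dosing stops increasingly reflect progression or later therapy. A short all-cause window limits that dilution. This is a good reason to keep the 30-day tables, but the SAP does not state it, and showing both windows meets it.
- *Decisions do not hang on these tables.* Escalation rests on DLTs in the first 28 days and on committee review of all available safety data. With cohorts this small, the listings let a reader find each late SAE. This limits the consequence to how completely the final report summarises safety.
- *Deaths.* A reader might also ask for a 100-day deaths table. All deaths are already tabulated without a window, so nothing is missing there.

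SAP Section 9 places the complete list of report analyses in a Data Presentation Plan, which was not available. Whether it adds 100-day SAE tables cannot be determined.

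**Conclusion.** The point holds as a reporting gap. No SAE summary, all-cause or drug-related, and no overall all-cause AE summary uses the 100-day window. SAE incidence as tabulated therefore omits 70 of the 100 post-dose days over which SAEs must be collected. Only non-fatal late SAEs judged unrelated and outside the OEOI terms are confined to listings. The other late SAEs are counted somewhere, but not as SAEs.

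The shifts of 33, 17 or 8 points are per subject, and assume that the subject's only SAE falls on days 31-100. The probabilities in the working rest on assumed rates and show a range, not a forecast. The change is worth making because it makes the primary safety summary more complete at little cost. It would not alter dose-escalation decisions.

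**What to change.** In SAP 7.6.2, repeat the SAE and drug-related SAE summaries with the 100-day window. In SAP 7.6.4, repeat the all-cause AE summary by worst grade with the same window. Keep the 30-day tables alongside. If the sponsor prefers 30 days only for these summaries, the SAP should say why.

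The cost is three repeated tables. The data are already collected, and the 100-day derivation already exists for drug-related AEs and OEOI. The downside is that the longer window admits more events caused by progression or subsequent therapy. Presenting both windows lets the reader see how much it adds. No change to the deaths tables is needed.

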8 CONVENTIONS

The following conventions may be used for imputing partial dates for analyses requiring dates:

- For missing and partial adverse event onset dates, imputation will be performed using the Adverse Event Domain Requirements Specification¹
- For missing and partial adverse event resolution dates, imputation will be performed as follows (these conventions may change):
 - If only the day of the month is missing, the last day of the month will be used to replace the missing day. If the imputed date is after the death date or the last known alive date, then the latest known alive date or death date is considered as the resolution date.
 - If the day and month are missing or a date is completely missing, it will be considered as missing.
- Missing and partial non-study medication domain dates will be imputed using the derivation algorithm described in 4.1.3 of BMS Non-Study Medication Domain Requirements Specification².
- For death dates, the following conventions will be used for imputing partial dates:
 - If only the day of the month is missing, the 1st of the month will be used to replace the missing day. The imputed date will be compared to the last known alive date and the maximum will be considered as the death date.
 - If the month or the year is missing, the death date will be imputed as the last known alive date.
 - If the date is completely missing but the reason for death is present, the death date will be imputed as the last known date alive.

- For date of progression after start of study therapy, the following conventions will be used for imputing partial dates:
 - If only the day of the month is missing, the 1st of the month will be used to replace the missing day. In case of the date of death is present and complete, the imputed progression date will be compared to the date of death. The minimum of the imputed progression date and date of death will be considered as the date of progression.
 - If the day and month are missing or a date is completely missing, it will be considered as missing.
- For date of progression to prior therapies, the following conventions will be used for imputing partial dates:
 - If only the day of the month is missing, the 1st of the month will be used to replace the missing day.
 - If the day and month are missing or a date is completely missing, it will be considered as missing.
- For other partial/missing dates, the following conventions were used:
 - If only the day of the month is missing, the 15th of the month will be used to replace the missing day.
 - If both the day and the month are missing, “July 1” will be used to replace the missing information.
 - If a date is completely missing, it will be considered as missing.

The following conversion factors will be used to convert days to months or years:

1 month = 30.4375 days and 1 year = 365.25 days.

Last known alive date will be defined based on all appropriate dates collected on the CRF.

All statistical analyses will be carried out using SAS (Statistical Analysis System software, SAS Institute, North Carolina, USA) unless otherwise noted.

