Documentation of extramedullary soft tissue plasmacytomas, if clinically indicated	X	Perform CT or MRI at screening if clinically indicated or if patient had a previous extramedullary or bone plasmacytoma.
[REDACTED]	[REDACTED]	[REDACTED]

Table 2-1: Screening Procedural Outline (CA025001)

Procedure	Screening Visit Within 28 days prior to treatment assignment	Notes
Adverse Event Reporting		
Monitor for Serious Adverse Events	X	All SAEs must be collected from the date of participant's written consent

Table 2-2: Treatment Phase Procedural Outline (CA025001)

Procedure	Cycle ^a 1				Cycle 2~	EOT ^b	Follow-up Period 28 days and 100 days post-last dose	Notes
	D 1	D 2	D 4	D 8				
Safety Assessments								
Physical Examination (PE)	X			X	X	X	X	
ECOG P.S.	X				X	X	X	
Physical Measurements ^c	X				X	X	X	Weight only Within 72 hours prior to dosing.
Vital Signs	X			X	X	X	X	See note in screening procedures and Section 9.4.2 . Cohort C1, C2: measure Pulse oximetry at rest and after exertion prior to nivolumab dosing
Electrocardiogram (ECGs) Refer to the DM ECG Study Guidelines	X				C2D1	X		See note in screening procedures and Section 9.4.3 . Pre dose and within 1 hour of completion of cabiralizumab dosing on C1D1 and C2D1
Laboratory Tests ^c	X			X	X	X	X	See note in screening procedures and Section 9.4.4 . Pre-dose on Day 1 on each cycle. Within 72 hours prior to dosing.
Pregnancy Test ^c	X				X	X	X	Every 2 cycles D1 within 72 hours prior to dosing
Adverse Event Reporting	X							

Table 2-2: Treatment Phase Procedural Outline (CA025001)

Procedure	Cycle ^a 1				Cycle 2~	EOT ^b	Follow-up Period 28 days and 100 days post-last dose	Notes		
	D 1	D 2	D 4	D 8	D 1					
Monitor for Non-Serious Adverse Events	X									
Monitor for Serious Adverse Events	X							All SAEs must be collected from the date of participant's written consent until 100 days of discontinuation of dosing		
Concomitant Medications Collection	X									
Pharmacokinetic (PK)/ADA Assessments										
Serial Blood PK Sampling	X	X	X	X	X ^d	X	X	See Section 9.5.		
ADA sampling	X				X ^e	X	X	See Section 9.5.		
Efficacy Assessments										
Tumor Assessments (for Solid tumor)	X					X ^f	Every 8 weeks (\pm 7 days) for first 48 weeks, then every 12 weeks (\pm 7 days) thereafter See Section 9.1.1			
For Multiple Myeloma										

Table 2-2: Treatment Phase Procedural Outline (CA025001)

Procedure	Cycle ^a 1				Cycle 2~ D 1	EOT ^b	Follow-up Period 28 days and 100 days post-last dose	Notes				

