8.3 Lost to Follow-Up

- All reasonable efforts must be made to locate participants to determine and report their ongoing status. This includes follow-up with persons authorized by the participant.
- Lost to follow-up is defined by the inability to reach the participant after a minimum of **three** documented phone calls, faxes, or emails as well as lack of response by participant to one registered mail letter. All attempts should be documented in the participant's medical records.
- If it is determined that the participant has died, the site will use permissible local methods to obtain date and cause of death.
- If investigator's use of third-party representative to assist in the follow-up portion of the study has been included in the participant's informed consent, then the investigator may use a Sponsor retained third-party representative to assist site staff with obtaining participant's contact information or other public vital status data necessary to complete the follow-up portion of the study.
- The site staff and representative will consult publicly available sources, such as public health registries and databases, in order to obtain updated contact information.
- If after all attempts, the participant remains lost to follow-up, then the last known alive date as determined by the investigator should be reported and documented in the participant's medical records.

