4.2.2.2 Duration of Response

Duration of Response (DOR) is defined as the time between the date of first documented response (CR or PR) to the date of the first documented tumor progression as determined by the investigator (per RECIST v1.1 criteria), or death due to any cause, whichever occurs first. Subjects who start subsequent therapy without a prior reported progression will be censored at the last evaluable tumor assessments prior to initiation of the subsequent anticancer therapy. Subjects who die without a reported prior progression will be considered to have progressed on the date of their death. Subjects who neither progress nor die, DOR will be censored on the date of their last evaluable tumor assessment. DOR will be evaluated for responders (confirmed CR or PR) only.

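### A death with a recorded year but no month is dated to last contact without checking the year, so the imputed date can contradict the record

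*SAP*

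**What the plan says.** SAP 8 gives separate rules for partial death dates.

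- **Day missing only.** The first of the recorded month is used, and then: "The imputed date will be compared to the last known alive date and the maximum will be considered as the death date". The recorded month is kept and last contact acts as a floor.
- **Month or year missing.** "If the month or the year is missing, the death date will be imputed as the last known alive date". Nothing is compared with a year that may have been recorded.
- **Whole date missing, reason for death present.** The last known alive date is used.

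The last known alive date is built from all appropriate CRF dates. For dates without a rule of their own, the clause beginning "If both the day and the month are missing" substitutes 1 July and so keeps the year. The section as a whole is permissive: "The following conventions may be used for imputing partial dates for analyses requiring dates".

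The death date then feeds two outputs. SAP 7.6.1 tabulates by cohort "Deaths within 30 days of last dose received, reasons for death", next to a table of all deaths and a by-subject death listing. In SAP 4.2.2.2, death is an event for duration of response (DOR): "Subjects who die without a reported prior progression will be considered to have progressed on the date of their death". SAP 4.2.3.2 has the same rule for the myeloma cohort.

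**The concern.** A recorded year is information. When it is later than the year of last contact, it proves that the subject did not die on the date the rule assigns. The day-missing rule just above avoids this kind of conflict by comparing the recorded part with last contact. The month-missing rule makes no such comparison.

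The visit schedule makes the 30-day row the exposed output. The follow-up column of Protocol Table 2-2 reads "Follow-up Period 28 days and 100 days post-last dose", so a subject seen at the first of these contacts and then lost has a last known alive date just inside the window. For a lost subject, Protocol 8.3 says: "If it is determined that the participant has died, the site will use permissible local methods to obtain date and cause of death". A death learned of indirectly is where a partial date is most likely.

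At stake is whether a death that the record places outside the window is reported as a near-treatment death, in cohorts of 3 to 12 subjects. For a responder, it is whether the listed DOR ends on a day that the recorded year rules out.

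**Working it through.** The plan states no figure on this point, so there is none to reproduce. The check is date logic. All calendar dates below are assumed examples, and within 30 days is read as day 30 or earlier.

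**1. General comparison.** Let L be the last known alive date, Y the recorded year of death and D the true, unknown date of death.

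- Current rule: imputed date = L.
- Comparison rule: imputed date = max(1 January of Y, L). This is the SAP's day-missing logic applied to the year.
- If the record is right, L ≤ D and 1 January of Y ≤ D. So L ≤ max(1 January of Y, L) ≤ D. The comparison date is never later than the true death and never further from it than L.
- If L falls in year Y, the two rules give the same date. If L falls in an earlier year, the current rule gives a date that the record contradicts.

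**2. Worked example.** Last dose 13 November 2017, L = 11 December 2017, death recorded as 2018.

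- Current rule: 13 November to 11 December = 17 + 11 = 28 days, so the death is counted within 30 days.
- Earliest date the record allows: 13 November to 1 January = 17 + 31 + 1 = 49 days, so it is outside the window.
- DOR, if this death is the event: 11 December to 1 January = 21 days provably lost.

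**3. When the output changes.** Four further assumed cases. DOR is in months of 30.4375 days (SAP 8), from a first response on 10 January 2018 where shown.

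| Last dose | L | Year of death | Current rule | Later of 1 January and L |
|---|---|---|---|---|
| 1 Dec 2018 | 29 Dec 2018 | 2019 | day 28, counted | day 31, not counted |
| 1 Nov 2018 | 29 Nov 2018 | 2019 | day 28, counted; DOR 323/30.4375 = 10.61 | day 61, not counted; DOR 356/30.4375 = 11.70 |
| 1 Jun 2018 | 29 Jun 2018 | 2018 | day 28, counted | day 28, counted |
| 1 Sep 2018 | 10 Dec 2018 | 2019 | day 100, not counted; DOR 334/30.4375 = 10.97 | day 122, not counted; DOR 356/30.4375 = 11.70 |

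A provable miscount in the 30-day row therefore needs L on or before day 30 and 1 January of the recorded year after day 30. If the 100-day contact took place, the row cannot be wrong.

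**4. How often the year helps.** Assume that last doses are spread evenly over 365 days, that L is day 28, and that death follows L by g days with the month unknown. Death falls in the next calendar year for g of the 365 last-dose dates. For two of these (L on 30 or 31 December), 1 January is still day 30 or 29, so the year proves a miscount for g − 2.

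| g (days) | Imputed date in wrong year, g/365 | Miscount provable, (g − 2)/365 |
|---|---|---|
| 10 | 2.7% | 2.2% |
| 30 | 8.2% | 7.7% |
| 60 | 16.4% | 15.9% |
| 120 | 32.9% | 32.3% |
| 180 | 49.3% | 48.8% |

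Every death in this table truly fell after day 30, and the current rule counts them all inside the window. The recorded year can correct only the share in the last column.

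**5. Effect of one death.** One subject is 1/3 = 33, 1/6 = 17 or 1/12 = 8 percentage points of a cohort of 3, 6 or 12. That is true of any single event and says nothing about how likely this one is.

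**The case against.** The strongest reply is that very little depends on this rule. Fatal events are SAEs, reportable within 24 hours and collected to 100 days after dosing ends (Protocol 9.2.1 and Appendix 3), and sites must try to obtain the date of death. A death with only a year should be rare among at most 36 subjects. The all-deaths table does not use the date, each death is listed by subject, and DOR is only listed, with no median or Kaplan-Meier estimate planned. The conventions are also permissive. All of this stands and limits the weight of the point. It does not defend the rule: where the years differ, the stated convention yields a date known to be false. The word may also leaves the choice open until after deaths are known.

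Three stronger readings are tempting, and the documents do not support them.

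- **That this is the only rule in SAP 8 that discards recorded information.** The rules for adverse event resolution, progression on study and progression on prior therapy also drop a known year when day and month are absent. They set the date to missing. What sets the death rule apart is that it substitutes a specific date that can contradict the record.
- **That DOR may be understated by most of a year.** The true date is unknown. The record proves only the gap from last contact to 1 January, which is 21 days in the first example, and no more than that can be recovered.
- **That deaths with no usable year should be taken out of the 30-day row.** Counting a death of unknown timing as near treatment is a cautious default in a safety table. Removing it is a separate and debatable choice.

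**Conclusion.** The point holds as a minor defect. For a death with a known year and unknown month, SAP 8 ignores the year. The imputed date contradicts the record whenever last contact was in an earlier calendar year.

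- The 30-day death row is provably wrong only if, in addition, last contact was by day 30 and 1 January of the recorded year is after day 30.
- DOR is shortened only for a confirmed responder who dies without reported progression and who was not already censored for subsequent therapy.

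A reader might infer that the death component of the primary safety endpoint is compromised. It is not, because the incidence of death is counted without reference to the date. The shares in the working rest on evenly spread last doses and last contact at day 28. They show when the recorded year can help and do not forecast how often such dates will occur.

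**What to change.** Replace the month-or-year clause in SAP 8 with wording such as:

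*Month missing, year recorded: the death date is the later of 1 January of the recorded year and the last known alive date. Year missing, or no part of the date available: the last known alive date is used.*

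Flag imputed death dates in the by-subject death listing of SAP 7.6.1. A reader can then see which entries in the 30-day row rest on imputation, including the same-calendar-year cases that the new wording cannot improve. No extra table row is needed.

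The cost is one or two sentences of SAP text, one listing flag and a few lines of programming, with no new data. Where last contact and death share a year the result is identical to the current rule, so nothing is lost. The change should be made before database lock.
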